We hypothesize that providing intermittent non-invasive positive pressure therapy (a form of NIV or PAP) with a handheld device to COPD patients immediately after exertion can relieve their dyspnea, and consequently allow them to be more active. This hypothesis will be tested by comparing the distance walked by COPD patients with the help of VitaBreath device versus Pursed Lip Breathing as measured by a modified 6-Minute Walk Test (6MWT).

The modified 6MWT will be a variation of the standard 6MWT^{32,29} where the participant will be stopped at the 3 minute mark to use the study device as intervention or controlled conditions for 30 seconds. Following this 30 seconds pause, the participant will continue with the remaining 3 minutes of the 6MWT. The distance walked by the participant for the entire 6 minutes will be recorded along with independent distances walked during the first and second 3 minute halves.

Although this product may have some anticipated benefit in the Pulmonary Rehab (PR) setting, this study is not intending to be directly associated with a PR program. Use of a similar environment may be coincidental and only to facilitate operational execution in a safe and monitored environment for the study.

STUDY INTERVENTIONS

VitaBreath (Investigational)

The Philips Resironics investigational device VitaBreath is a handheld, battery powered, intermittent positive airway pressure device that is non-invasive, and provides positive airway pressure (PAP) of 18 cm H₂O during inspiration and 8 cm H₂O on expiration, thus creating 10 cm H₂O of pressure support. Pressure support is defined as the difference between inhalation pressure and exhalation pressure. **The study device is intended as an adjunct therapy to relieve shortness of breath in COPD patients who experience exertion-related dyspnea to allow them to be more active.** The air is delivered to the patient via a mouthpiece on the device.

The VitaBreath is not intended to replace participant's bronchodilators, anti-inflammatory medicines, and/or supplemental oxygen. It is not intended to replace pulmonary rehabilitation as well.

The VitaBreath device is designed for non-continuous use only and typical device use is expected to be for 2-3 minutes. The device should only be operated for less than 10 minutes at a time. After such time, the device should be turned off for at least 30 minutes.

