Participants with a diagnosis of COPD who experience shortness of breath may be eligible for participation in this study

Sample Size

This will be a 20 patient pilot study to provide a power analysis for the Pivotal IDE protocol. The previous engineering clinical study included three treatment conditions, whereas the planned pivotal design will only have two conditions, VitaBreath and pursed-lip breathing. This pilot study will test this new trial design.

Inclusion / Exclusion Criteria:

Inclusion Criteria	Exclusion Criteria

All participants:
 
• Age ≥ 40• Ability to provide consent• COPD diagnosis• FEV₁ <55 and ≥ 25 percent of predicted value• Perceived Shortness of Breath via the Modified Medical Research Counsel Dyspnea questionnaire (rating of 2 or greater) (Appendix B)• Able to follow directions• Able to tolerate mild physical activity• Pursed Lip Breathing as standard of care• No evidence of bullous lung disease (with any bullae greater than 3cm in diameter) as confirmed by a CT scan within the past one year.	
All participants:
 
• Subjects who are acutely ill, medically complicated or who are medically unstable as determined by the investigator.• Suffering from COPD exacerbation at time of enrollment or 60 days prior• Subjects who are not currently prescribed oxygen and manifest oxygen desaturation below 88% on the screening 6MWT• Subjects with heart disease or neuromuscular disease.• Subjects who are not prescribed short-acting bronchodilator medication• Patients who have experienced recent barotrauma or pneumothorax• Unstable angina or Myocardial Infarction during past month• Uncontrolled Hypertension (systolic blood pressure of >180mmHg and a diastolic >100mmHg)• Heart Rate >120 at rest• Subjects who have trouble coordinating their breathing with the device during the device training, or cannot tolerate the device mouthpiece resulting in leaks from the nasal cavity• Women of child-bearing potential (WOCP) who are pregnant, breast-feeding, or planning pregnancy during the course of the study. (WOCP must have a negative pregnancy test at every visit)

Pilot Study to Assess the Effect of Providing Intermittent Positive Airway Pressure in COPD Patients in
Order to Relieve Their Exertion Related Shortness of Breath
HRC-17007-VBIDEPILLOT-PN

Pregnancy Screening

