The participant's medical history will include an assessment of their medication use, smoking history, and how often they rely on their rescue medication (at rest and with exertion). Any participation in a Rehabilitation Program will be captured as well.

Participants will be allowed to begin exercise assessments 15 minutes after their bronchodilator administration. Concomitant medication and any adverse events will be recorded. The Participants oxygen level will be monitored during the standard 6MWT by continuous finger pulse oximetry. If the participant is not currently prescribed and using supplemental oxygen and their oxygen level is

Pilot Study to Assess the Effect of Providing Intermittent Positive Airway Pressure in COPD Patients in Order to Relieve Their Exertion Related Shortness of Breath

HRC-17007-VBIDEPILOT-PN

consistently \leq 88% during the test, the test will be stopped and the participant will be excluded. If the participant is currently prescribed and using supplemental oxygen during the test and their oxygen level consistently falls \leq 88%, supplemental oxygen will be titrated during the test by trained study staff until their oxygen level persistently is at 90% or higher during the test. Oxygen equipment will be available at the sites.

We will follow the American Thoracic Society Statement Guidelines for the Six-Minute Walk Test which include the following criteria for immediately stopping a 6MWT: Intolerable dyspnea, leg cramps, staggering, diaphoresis, and pale or ashen appearance.

Device Training

Participants will be asked to train on the VitaBreath device to practice breathing with it. The purpose of this training period is to get the participant acclimated to the device prior to using it during the modified 6MWTs at the Study Intervention Visit. If the participants have trouble coordinating with the device or cannot tolerate the mouthpiece resulting in leaks from the nasal cavity, they will be excluded from the study.

All participants will also be asked to practice pursed lip breathing with proper instruction and training by site staff.

Randomization

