If the participant qualifies for the study, their device usage order (VitaBreath or control condition/ pursed lip breathing) will be randomized using a permuted-block randomization sequence at the study intervention visit. Each participant will complete two modified 6MWTs during the Study Intervention Visit, one with each therapy in a randomized order. The randomization will be stratified within each site.

Sites will use a randomization schedule in order to randomize the patients.

The Study Intervention Visit will be scheduled within 5 ± 2 business day period of Screening Visit/s.

Study Intervention Visit – Modified 6MWT

During the study intervention visit, the participants will first complete the Chronic Respiratory Questionnaire (CRQ)³³- initial (CRQ) (Appendix C). This survey will be completed by participants before they use the device during the modified 6MWT. The response to this questionnaire will serve as a baseline measurement.

At the Study Intervention Visit, WOCP will complete a pregnancy urine test prior to any usage of the VitaBreath study device.

Participants will be asked to practice breathing again with the VitaBreath device to get acclimated prior to using it during the modified 6MWTs at the Study Intervention Visit. Such use will be for a maximum time of 5 – 10 minutes. The coordinator will also remind the participant to practice Pursed Lip Breathing.

Pilot Study to Assess the Effect of Providing Intermittent Positive Airway Pressure in COPD Patients in Order to Relieve Their Exertion Related Shortness of Breath

HRC-17007-VBIDEPILLOT-PN

The participants will be asked to wait 30 minutes after using the device to wash-out any effects of training with the device before starting the 6MWT.

The coordinator will assess AEs or medication changes since the last visit. Resting Heart Rate and Blood pressure will be checked before the 6MWTs.

Participants will be asked to take their short acting bronchodilator medication after the device training, but only before the first walk test. Participants will be allowed to begin assessments 15 minutes after their bronchodilator administration. Concomitant medication and any adverse events will be assessed. If additional uses of the bronchodilator are required by participants during the in lab study, that use will be recorded / documented. Participant's blood oximetry levels will be monitored via pulse oximeter at all times.

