A medically trained clinician will be present during the test in case of adverse events.

Participants will be asked to perform two 6MWT assessments on the Study Intervention Visit. Borg assessments will be made prior to the start of each test.

For one of the tests, participants will be given the VitaBreath device and the other test will be with control condition, where the patients will be instructed to use pursed lip breathing. The order of these two tests will be randomized.

Test Procedure

In order to standardize the participant use of the devices, at the 3 minute mark the test will be stopped for 30 seconds. During this 30 second pause, study participants will be instructed to use the study device in order to help them recover from being short of breath. For the test where participants are randomized to not use a device, they will be instructed to use the pursed lip breathing technique to help them recover during the 30 second duration. After the 30 second pause, the participants BORG assessment will be made and then they will be instructed to complete the remaining 3 minutes of the walk test. At the end of the test, participants will be asked to sit down and their Borg assessment will be made every 30 seconds until they reach their baseline Borg.

Participants will be required to rest at least 30 minutes between tests.

Statistical and Analytical Plan

Descriptive Data

Descriptive data tables will be provided for all variables of interest. Continuous data will be presented by mean, standard deviation, median, minimum and maximum observation. Data will be presented in the untransformed and transformed format (if applicable) for each continuous variable. Categorical data will be presented as frequencies and percentages.

Pilot Study to Assess the Effect of Providing Intermittent Positive Airway Pressure in COPD Patients in
Order to Relieve Their Exertion Related Shortness of Breath
HRC-17007-VBIDEPILLOT-PN

Analysis Populations

The endpoint will only be analyzed among completed cases in this pilot study.

Primary Effectiveness Analysis

The data from this trial will be evaluated to determine whether they meet the assumptions of parametric methods. The distance walked during the modified 6MWT will be compared between VitaBreath and pursed-lip breathing, using either a paired t-test or the nonparametric Wilcoxon Signed Ranks test, depending on the distribution of the data. The significance level will be a two-sided alpha of 0.05.

Safety Analysis

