The incidence of adverse events will be tabulated in the descriptive statistics and compared between the treatment conditions.

Subject Accountability and Missing Data

It is expected that the number of subjects who will withdraw early from this pilot study will be small. The number and proportion of subjects eligible for and compliant with the final examination will be presented. Subjects who withdraw from the study will be tabulated with the reasons for the withdrawal. The endpoint will only be analyzed among completed cases in this pilot study, and therefore data will not be imputed for missing values.

Interim Analysis

There is no interim analysis planned for this study.

Statistical Software

The statistical analyses will be done using SAS, SPSS, StatXact, or Systat. Each of these software packages provides special features that will be exploited to provide a comprehensive analysis with excellent graphics support.

RISK AND DISCOMFORTS

The FDA has determined that this study is significant risk due to the target patient population. VitaBreath is intended to be an adjunct therapy for COPD participants to utilize for relief of their dyspnea after exertion that can consequently allow them to be more active. VitaBreath delivers intermittent non-invasive positive pressure (PAP) therapy that provides positive airway pressure of 18 cm H₂O during inspiration (IPAP) and 8 cm H₂O on expiration (EPAP), with a handheld device to COPD participants.

Pilot Study to Assess the Effect of Providing Intermittent Positive Airway Pressure in COPD Patients in Order to Relieve Their Exertion Related Shortness of Breath

HRC-17007-VBIDEPILLOT-PN

We believe that although there may be discomforts associated with the use of this device, all of the study devices have been tested to help ensure safety. Should the equipment not perform as designed, ventilation could increase or decrease more than desired. This effect could be uncomfortable. The participant can easily remove the device should it become uncomfortable or make breathing difficult. Other potential side effects may include ear discomfort, and gastric distension (aerophagia), all of which are quite uncommon, but generally cited side effects of PAP therapy.

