Appendix B

Modified MRC Dyspnea Scale	
0	Breathless only with strenuous exercise
1	Short of breath when hurrying on the level or walking up a slight hill
2	Slower than most people of the same age on the level because of breathlessness or have to stop for breath when walking at my own pace on the level
3	Stop for breath after walking about 100 meters or after a few minutes at my own pace on the level
4	Too breathless to leave the house or I am breathless when dressing

Pilot Study to Assess the Effect of Providing Intermittent Positive Airway Pressure in COPD Patients in
Order to Relieve Their Exertion Related Shortness of Breath
HRC-17007-VBIDEPILOT-PN

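### Does limiting the endpoint to completed cases drop walks stopped for breathlessness and so distort the pilot's inputs to the pivotal power analysis?

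*Combined protocol and SAP*

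**What the plan says.** Under Analysis Populations, the efficacy analysis is restricted in one sentence: "The endpoint will only be analyzed among completed cases in this pilot study". Subject Accountability and Missing Data repeats the restriction and adds "therefore data will not be imputed for missing values". That section also expects few early withdrawals, tabulates withdrawals with their reasons, and reports how many participants were compliant with the final examination. Neither section defines a completed case.

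Study Procedures (screening) and Risk and Discomforts (exercise testing in general) both list "criteria for immediately stopping a 6MWT: Intolerable dyspnea, leg cramps, staggering, diaphoresis, and pale or ashen appearance". Study Objectives defines the primary endpoint as distance walked in the modified 6MWT and sets no minimum duration. Background Significance says "The distance walked by the participant for the entire 6 minutes will be recorded", and the same sentence goes on to require the separate distance for each three-minute half. The primary test is a paired t-test or Wilcoxon signed-ranks test at two-sided 0.05. Sample Size gives the purpose: "This will be a 20 patient pilot study to provide a power analysis for the Pivotal IDE protocol".

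**The concern.** A walk cut short by intolerable dyspnea is an outcome of the breathing method under test. Some of the protocol's wording could suggest that such a walk is not completed. Randomization says "Each participant will complete two modified 6MWTs during the Study Intervention Visit", Test Procedure says of the period after the pause that "they will be instructed to complete the remaining 3 minutes of the walk test", and no value is stated for a shorter walk. An analyst who took completed to mean the full six minutes in both walks would discard the whole pair, although the metres reached before the stop are valid data.

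Early stops are also plausible. Entry requires a modified MRC grade of 2 or more, and grade 3 reads "Stop for breath after walking about 100 meters or after a few minutes at my own pace on the level". The exclusion criteria remove people who desaturate on the screening walk, but do not name people who stop it because of dyspnea.

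The pivotal power analysis would be at stake. Dropping stopped walks tends to understate the SD of the paired difference when the stops are discordant between conditions. It also biases the mean against the device if more stops fall on pursed lip breathing, and in its favour if more fall on the device.

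**Working it through.** **Which reading the text supports**

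- The missing-data section places completed cases beside withdrawal and draws from the term the consequence that nothing is imputed. In that setting a completed case is one whose endpoint is not missing.
- The endpoint is distance walked. A walk stopped at minute 4 has a distance.
- In Background Significance the full six minutes is contrasted with the two halves. The phrase separates the total from its parts and does not make duration a condition for having a value.
- The verb complete is used procedurally elsewhere: participants also complete a questionnaire and a pregnancy test.
- A paired test needs two values per participant. Two recorded distances supply them.
- No section calls a stopped walk missing, invalid or a withdrawal.

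**What the other reading would cost**

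The only input from the documents is n = 20. The rest are assumptions: mean benefit 10 m and SD 30 m in full-time walkers, six-minute distance 300–400 m, stops at minute 4 or 5.

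Distance lost per stop: L = (distance/6) × (6 − stop minute), giving 50, 66.7, 100 or 133.3 m.

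With *a* participants stopped on pursed lip breathing, *b* others stopped on the device, and k = a + b, the stopped differences are 10 + L and 10 − L:

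- mean = [(20 − k) × 10 + sum of stopped differences] / 20
- SS = (19 − k) × 900 + (20 − k)(10 − mean)² + Σ(stopped difference − mean)²
- SD = √(SS/19)

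Pivotal sample size is roughly proportional to (SD/mean)². With stopped walks dropped this is (30/10)² = 9.0. With the distance at the stop kept:

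| Stops (PLB, device) | Mean, m | SD, m | (SD/mean)² |
|---|---|---|---|
| 2, 0 | 15.0 to 23.3 | 32.3 to 49.9 | 4.4 to 4.6 |
| 1, 1 (different people) | 10.0 | 32.7 to 51.7 | 10.7 to 26.8 |
| 0, 2 | 5.0 to −3.3 | 32.3 to 49.9 | no useful value once the mean nears 0 |

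Example for (2, 0) with L = 50: mean = (18 × 10 + 2 × 60)/20 = 15.0; SS = 17 × 900 + 18 × 25 + 2 × 2025 = 19,800; SD = √(19,800/19) = 32.3; ratio = (32.3/15)² = 4.63. Dropping the two pairs would make the pivotal trial about 9.0/4.63 = 1.9 times as large as needed.

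The (1, 1) row puts the two stops in different people. If one very breathless participant stops both walks at about the same minute, the losses cancel and the difference stays near 10 m. The mean is then 10 m and SD = √(18 × 900/19) = 29.2 m, essentially unchanged.

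A simulation let the same patients tend to stop in both conditions. It assumed a mean distance of 300 m, between-patient SD 80 m, the same 10 m and 30 m, stops spread over the second half, and a pivotal paired t-test with 80% power. Pivotal N with stops kept versus dropped:

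| Stop rate (PLB / device) | Kept | Dropped |
|---|---|---|
| 0% / 0% | 73 | 73 |
| 5% / 5% | 90 | 73 |
| 10% / 5% | 64 | 73 |
| 20% / 5% | 40 | 74 |
| 5% / 10% | 335 | 73 |

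**Scale against sampling error**

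With 20 pairs and SD 30 m, the 95% half-width for the mean is 2.093 × 30/√20 = 14.0 m. The 95% interval for the SD is 30√(19/32.85) to 30√(19/8.91), or 22.8 to 43.8 m. The shift in the mean from two stops on one condition is 5.0 to 13.3 m, within that uncertainty.

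**The case for a change.** The strongest case for a change is that the rule is unwritten, the data would be seen before it was settled, and writing it down would cost two or three sentences. Calling the study a pilot does not dispose of this, because its outputs feed the pivotal sample size and one or two exclusions out of 20 can move them. The expectation of few withdrawals does not help either, since a stopped walk is not stated to be a withdrawal. If walks were dropped and stops were unequal, the bias would be real. That it lies within sampling error does not remove it.

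This much stands: the term is undefined, and the arithmetic for the restrictive reading is correct. That reading, however, needs the analyst to discard a recorded value of the primary endpoint, and no section asks for that. The evidence on stop frequency is also thin. Grade 3 describes resting for breath, which is not a terminated test. Entry also requires tolerance of mild physical activity, a bronchodilator is taken before walking, and each modified walk has a 30-second recovery pause. Stops remain possible, at an unknown rate.

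The obvious alternative, analysing everyone who starts both walks and using the distance reached, would still leave out anyone unable to begin the second walk. For participants with two recorded distances it gives the same result as the plan on its natural reading.

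**Conclusion.** The concern does not call for a change. Completed cases is best read as participants who did not withdraw and have a recorded distance in both walks. On that reading a walk stopped early contributes the metres reached, no selection on outcome occurs through stopped walks, and the pilot's mean and SD are those a revised rule would give. The effect on the analysis is then zero.

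The conclusion rests on the analyst using recorded distances as the endpoint values. If stopped walks were instead excluded, the pivotal sample size could err in either direction, mainly when stops are discordant between a participant's two walks. The documents cannot size that error, and every metre figure in the tables is an assumption. What remains is a missing definition that competent analysts would fill sensibly.

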Participants will be instructed that the device is intended to provide effective relief of dyspnea. It will be further communicated to them that the device may or may not help them recover from shortness of breath.

The VitaBreath device is intended to relieve exertion-related shortness of breath in COPD patients. For the majority of patients, this would occur as a result of activities of daily living, such as retrieving the

Pilot Study to Assess the Effect of Providing Intermittent Positive Airway Pressure in COPD Patients in Order to Relieve Their Exertion Related Shortness of Breath

HRC-17007-VBIDEPILOT-PN

mail or climbing stairs. Although patients may use the device when participating in an exercise program that is not the primary intended use of the device.

Pursed Lip Breathing (Control condition)

Pursed lip breathing (PLB) is the standard of care and will be used as the control condition comparator.

STUDY DESIGN

This will be laboratory-based study with a 2-arm, randomized, controlled, crossover design where the participants will be tested with the investigational device VitaBreath and control condition (PLB) in a random order.

STUDY AIM

The aim of this study is to evaluate that intermittent positive airway pressure therapy given to COPD patients with the VitaBreath device will relieve their exertional dyspnea allowing them to walk further in a modified 6MWT.

STUDY OBJECTIVES

The primary objective will be to compare the distance walked in 6 minutes by COPD participants using Pursed Lip Breathing (PLB) versus an intermittent positive airway pressure handheld device, VitaBreath.

Primary Efficacy Endpoint: Distance walked as measured by modified 6MWT evaluated during the Study Intervention Visit

Primary Hypothesis

Participants will walk further during the modified 6-Minute Walk Test when using VitaBreath compared to pursed-lip breathing at the Study Intervention Visit.

SUBJECT SELECTION / ENROLLMENT

Participants will be identified by investigators at each site. Following IRB approval and after obtaining written informed consent, participants found to possibly meet criteria for participation will be screened to determine their eligibility. The inclusion and exclusion criteria of this study are listed below.

Pilot Study to Assess the Effect of Providing Intermittent Positive Airway Pressure in COPD Patients in
Order to Relieve Their Exertion Related Shortness of Breath
HRC-17007-VBIDEPILOT-PN

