All women of childbearing potential, (defined as any woman, unless surgically sterile or postmenopausal for at least 1 year) must be instructed to contact the Investigator immediately if they suspect they might be pregnant while participating in this study. If a participant becomes pregnant, she will be discontinued from the study. Pregnancy urine tests of WOCP will be completed at each visit prior to CT scan or usage of the VitaBreath study device.

STUDY PROCEDURES

The study will be explained to the potential participant and sufficient time provided to the subject to ask questions regarding the study. Study related procedures will commence only after the informed consent is signed by the subject. This is a multi (2 or 3) visit study as part of which, participants will be asked to complete in-lab six minute walk tests.

Screening Visit/s 1 and 2 - Screening and Randomization

Recruited participants will be asked to report to the clinical site where consenting and screening related procedures will take place. After consenting, subject eligibility will be evaluated and the following will be collected, demographics, anthropometric measurements, concomitant medications, vital signs and medical history review at Screening Visit 1. WOCP will complete a pregnancy urine test at Screening Visit 1 prior to any CT scan.

The rest of the screening procedures may commence if a recent CT scan (in the past year) of the participant is available and confirms eligibility. If the study participant has not had a CT scan within the past year, they will be scheduled for one by study staff. The participants will be asked to return for Screening Visit 2 once the CT scan review confirms their eligibility.

If a Screening Visit 2 is required, WOCP will complete a pregnancy urine test prior to any usage of the VitaBreath study device at Screening Visit 2.

Upon confirmation of their CT scan review at either Screening Visit 1 or if needed, Screening Visit 2, participants will undergo the remaining screening procedures to assess study eligibility: spirometry, 6 minute walk test (Standard 6MWT)^{29,32}, device training/acclimation, and a dyspnea rating assessment (Modified Medical Research Counsel - Appendix B)³⁴.

Participants will be asked to take their short-acting bronchodilator medication 15 minutes prior to start of the 6MWT.

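### The randomised crossover is tested with a paired t-test or signed-rank test that ignores walk order, so any walk-1 to walk-2 difference inflates the error variance; a period term costs little

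*Combined protocol and SAP*

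**What the plan says.** Study Design describes a "2-arm, randomized, controlled, crossover design where the participants will be tested with the investigational device VitaBreath and control condition (PLB) in a random order". The Randomization section adds: "Each participant will complete two modified 6MWTs during the Study Intervention Visit, one with each therapy in a randomized order". The order of conditions "will be randomized using a permuted-block randomization sequence at the study intervention visit", stratified by site. Block size and number of sites are not given.

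Primary Effectiveness Analysis compares the distance walked under the two conditions "using either a paired t-test or the nonparametric Wilcoxon Signed Ranks test, depending on the distribution of the data", at a two-sided 0.05 level. Only completed cases are analysed. The statistical section contains no period, sequence or carryover term and no summary by order.

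Two procedural details bear on whether the walks are interchangeable. Under Study Intervention Visit – Modified 6MWT: "Participants will be asked to take their short acting bronchodilator medication after the device training, but only before the first walk test". Under Test Procedure: "Participants will be required to rest at least 30 minutes between tests".

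Sample Size sets 20 patients and says the pilot is to supply the power analysis for the pivotal study. It states no effect size, SD, power or pivotal test.

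**The concern.** Order is randomised and then not used in the analysis. The two walks differ by design. The planned bronchodilator dose comes before walk 1 only, so walk 2 starts further from it. Walk 2 also follows an earlier exertion and a first attempt at the modified test with its mid-walk stop. The screening walk is a standard six-minute walk, so it does not rehearse that stop. A shift between walks is therefore plausible, though the documents give neither its size nor its direction.

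If there is such a shift, the within-participant treatment difference is centred at a different value in each order. The paired test counts that spread as noise. The confidence interval widens, power falls and the reported SD is too large. If the analysed orders are unequal in number, part of the shift also enters the estimate. The SD matters here because planning the pivotal study is the pilot's stated purpose.

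**Working it through.** **Inputs from the documents.** n = 20; two-sided alpha 0.05; two orders; two walks at one visit; completed cases only. The sample size cannot be reproduced, because no effect, SD or power is given for it.

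**Assumptions.** Normal within-participant differences; no carryover; SD of the difference σ = 1 within each order; true effect τ = 0.660σ, which gives the paired t-test 80% power at n = 20 when there is no period effect. Let p be the walk-2 minus walk-1 effect and r = p/σ.

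**Timing.** Walk 2 starts at least 3 + 0.5 + 3 + 30 = 36.5 minutes after walk 1 started.

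**Model.** For D = distance with VitaBreath minus distance with pursed-lip breathing:
- VitaBreath first (n1 participants): D has mean τ − p
- pursed-lip breathing first (n2 participants): D has mean τ + p

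**Paired analysis.** The mean of D is τ + p(n2 − n1)/n. At 10:10 it is unbiased. At 11:9 it shifts by 0.1p and at 12:8 by 0.2p, with the sign depending on which order is larger. The shift is conditional on the realised split and averages to zero over randomisation. At 10:10 the expected variance of D is σ²[1 + r²·n/(n − 1)] = σ²[1 + r²·20/19].

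**Adjusted analysis.** Average the two order-specific means of D. The variance is (σ²/4)(1/n1 + 1/n2), with 18 degrees of freedom instead of 19. The critical t moves from 2.093 to 2.101 (+0.4%). At 10:10 the variance is σ²/20, as for the paired mean without a period effect.

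**Results at 10:10.** Power and type I error come from simulation: 200,000 trials per cell for the t-tests and 100,000 for the rank tests. Independent runs agreed within simulation error.

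| r | Variance factor | Apparent SD | Paired t: 95% CI half-width | Paired t: power | Paired t: type I error | Signed-rank power |
|---|---|---|---|---|---|---|
| 0 | 1.00 | 1.00 | 2.093/√20 = 0.468σ | 80% | 0.05 | 78% |
| 0.25 | 1.07 | 1.032 | 0.483σ | 78% | 0.044 | 76% |
| 0.5 | 1.26 | 1.124 | 0.526σ | 72% | 0.029 | 69% |
| 1 | 2.05 | 1.433 | 0.671σ | 49% | 0.006 | 43% |

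At every r the adjusted t-test keeps about 80% power, 5% type I error and a half-width of 2.101/√20 = 0.470σ. The rank-sum test on period differences has about 75% power throughout.

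**Unequal orders, r = 0.5.**
- 11:9: paired power is 79% or 65% depending on which order is larger; adjusted 79%.
- 12:8: paired power is 85% or 57%; adjusted 78%. Paired type I error is about 0.045 (0.030 at r = 1).
- Paired type I error exceeds 5% only from 13:7: about 0.055, 0.066 and 0.075 at r = 0.25, 0.5 and 1.

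**How likely are such splits?** Assume 2 to 5 sites with random accrual, before dropout. With blocks of 4, the chance of 11:9 or worse is 38–61%, of 12:8 or worse 1–13%, and of 13:7 or worse 0–1%. Across block sizes 2, 4 and 6, 12:8 or worse has probability 0–22% and 13:7 or worse 0–4%.

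**Cost of adjusting when r = 0.** T-test power goes from 80.0% to 79.8% at 10:10, 79.4% at 11:9 and 78.1% at 12:8. The effect detectable with 80% power at 10:10 goes from 0.660σ to 0.663σ. For the rank tests at 10:10, 77.9% (signed-rank) becomes 75.3% (rank-sum).

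**Pivotal sample size.** If the unadjusted SD were used to size a period-adjusted pivotal test, N would be too large by the variance factor: ×1.07, ×1.26 or ×2.05. As an illustration with assumed values, σ = 40 m and p = 20 m give an apparent SD of √(1600 + 400·20/19) = 45.0 m and a factor of 1.26.

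**The case against.** The planned analysis is not wrong. It is unbiased over randomisation and conservative near balance, and blocking within site makes 13:7 unlikely. This is a 20-patient pilot with no power target, and a modest period effect (r = 0.25) costs 2 power points and 3% on the SD. The large losses need r near 1, which nothing in the documents supports.

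The protocol also limits period effects. There is a standard six-minute walk at screening and practice with both techniques. Participants are "asked to wait 30 minutes after using the device to wash-out any effects of training with the device before starting the 6MWT". They rest between walks, and Borg scores are followed until they return to baseline. No duration of action is given for the bronchodilator, so the extra 36.5 minutes may not matter; additional uses during the visit are foreseen and recorded.

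The change is not free for both tests. The rank-sum test has less power than the signed-rank test until r is about 0.3, and the adjusted t-test loses about 4 points at 13:7 (75.8% against 79.8% at 10:10).

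The effect on pivotal N is doubly conditional: it needs a sizeable r and an unadjusted SD used to size an adjusted test. The error would be an oversized trial, and the within-sequence SD can be computed from the same data.

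All of this stands as a limit on the size of the harm. It does not remove the omission. The listed precautions reduce a period effect without excluding one, and estimating variability for the pivotal study is what the pilot is for. Choosing the adjustment after seeing the data would weaken the primary result.

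**Conclusion.** The concern holds. The randomised order is not used in the analysis, and at equal splits any period effect goes wholly into the error variance; at unequal splits part of it also moves the estimate. This is a loss of efficiency and an inflated SD, not a false-positive problem of practical size.

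At 10:10 the paired t-test loses about 2, 8 and 31 power points at r = 0.25, 0.5 and 1. These figures rest on an assumed r, normal differences, no carryover and an effect set to give 80% power; r = 1 should be read as an extreme case. The low cost of adjusting does not depend on any assumed period effect. It is small for the t-test at or near balance and somewhat larger for the rank test. If the pivotal study keeps the paired test, its N would fit that test and the cost is lost efficiency only.

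**What to change.** In Primary Effectiveness Analysis, replace the two named tests with the following:

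- **Primary model:** distance walked, with fixed effects for treatment, period and sequence and a random participant effect. With completed cases this is equivalent to a two-sample t comparison of within-participant period differences (walk 1 minus walk 2) between the two orders; half the difference in means estimates the treatment effect.
- **Nonparametric counterpart:** the rank-sum test on the same period differences.
- **Reporting:** the treatment difference with 95% confidence interval, distances by order and walk, the number analysed in each order, and the pooled within-sequence SD of the treatment difference. State whether that SD is the one to be used in the pivotal power analysis and which pivotal test it is meant for.
- **Limitation:** state that the period term does not address carryover.

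This is SAP wording only, with no new data or procedures. It costs one residual degree of freedom (18 instead of 19) and, if there is no period effect, the small power losses shown in the working.
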